7.3.3 Clinical Adjudication Committee

A Clinical Adjudication Committee (CAC) will evaluate the following events for the purposes of confirming them according to the criteria in Section 8.0 – Statistical Analysis Plan, as well as evaluating the presence of confounding factors.

- 1) Antitumor response (e.g., PFS, ORR, DOR) assessment based on IMWG criteria [1] including confirmation of disease progression.

The following information will be submitted by the Sponsor to the CAC for their review:

- The subject's myeloma laboratory results.
- All imaging results
- Local pathology results including results of bone marrow samples for confirmation of CR or sCR.

The role of the CAC is to ensure that all treatment outcomes are judged uniformly, using standard criteria and processes. The CAC will be composed of 3 members who are qualified by training and experience to evaluate MM disease progression and response assessment according to IMWG criteria [1] using data provided by the Sponsor. The specific data provided, and the timing of the reviews, will be described in the Adjudication Charter.

All personnel involved in the adjudication process will remain blinded to treatment allocation throughout the trial. Specific details regarding endpoint definitions can be found in the Adjudication Charter.

8.0 STATISTICAL ANALYSIS PLAN

This section outlines the statistical analysis strategy and procedures for the study. If, after the study has begun, changes made to primary and/or key secondary hypotheses, or the statistical methods related to those hypotheses, then the protocol will be amended (consistent with ICH Guideline E-9). Changes to exploratory or other non-confirmatory analyses made after the protocol has been finalized, but prior to the conduct of any analysis, will be documented in a supplemental SAP (sSAP) and referenced in the Clinical Study Report (CSR) for the study. A separate PK analysis plan as well as biomarker analysis plan will be provided. Post hoc exploratory analyses will be clearly identified in the CSR. The PRO analysis plan will also be included in the sSAP.

On 03-JUL-2017, the US FDA placed KN183, KN185 and cohort 1 of KN023 on clinical hold based on safety data from KN183 and KN185 presented to the DMC. The FDA determined that the risks of pembrolizumab plus pomalidomide or lenalidomide outweighed any potential benefit for patients with multiple myeloma. Based on this decision, the treatment phase of KN183 and KN185 is closed effective immediately. All subjects must stop study treatment, complete the Discontinuation Visit and move into the long-term safety and survival follow-up per protocol.

Due to the current status of the study the statistical analysis of this section may be modified and will be reported in the CSR.

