- f. Myeloma laboratory testing should be performed in the follow-up period for all subjects who discontinue study treatment for reasons other than disease progression.
- g. Pre-dose trough PK and anti-pembrolizumab antibody samples will be collected at C1D1, C1D22, C2D15, C5D15 and every 4 pembrolizumab infusions thereafter, and 30 days after discontinuation of study drug (or until the subject starts new anti-cancer therapy). Pharmacokinetic/anti-drug antibody (PK/ADA) samples may be used to conduct additional safety analysis, if needed.
- h. This sample should be drawn for planned analysis of the association between genetic variants in DNA and drug response. If there is either a documented law or regulation prohibiting collection, or if the IRB/IEC does not approve the collection of the sample for these purposes, then this sample will not be collected at that site. If the sample is collected, leftover extracted DNA will be stored for future biomedical research if the subject signs the FBR consent. If the planned genetic analysis is not approved, but FBR is approved and consent is given, this sample will be collected for the purpose of FBR.
- i. Patient reported outcomes (PROs) are assessed on day 1 of Cycle 1 (every 28-day cycle) through Cycle 4 and then every 3 cycles (i.e., Cycle 7, 10, 13, etc.) while the subject is receiving study treatment, at treatment discontinuation, and at 30 days post treatment discontinuation (post-treatment safety follow-up).
- j. Whole blood for correlative studies (RNA/DNA) should only be collected at C1D1, C2D1 and at discontinuation.
- k. Cycle 1 treatment must be administered within 3 calendar days of randomization number assignment in IVRS/IWRS, after ensuring subjects meet disease criteria through previous consultation with the Sponsor.
- l. The Lenalidomide Education and Counseling Guidance Document must be completed for all subjects and signed by a trained counselor prior to each dispensing of lenalidomide in accordance with the REVLIMID REMS™/country-specific risk mitigation program. A copy of this document must be maintained in the subject's records for each dispense for all countries/sites where lenalidomide is provided centrally by the Sponsor.

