8.6 STATISTICAL METHODS

8.6.1 Statistical Methods for Efficacy Analyses

This section describes the statistical methods that address the primary and secondary objectives. Methods related to exploratory objectives and exploratory endpoints will be described in the supplemental statistical analysis plan (sSAP), this includes the ePRO data described in 7.1.2.9 and minimum residual disease (MRD). In addition, a separate SAP will describe the analysis of PK data described in Section 7.1.3.2

Efficacy results that will be deemed to be statistically significant after consideration of the Type I error control strategy are described in Section 8.7 Interim Analysis and Section 8.8, Multiplicity. Nominal p-values will be provided for other efficacy analyses but should be interpreted with caution due to potential issues of multiplicity.

Progression-free Survival (PFS)

The non-parametric Kaplan-Meier method will be used to estimate the PFS curve in each treatment group. A stratified Cox proportional hazards model with Efron's method of tie handling will be used to assess the magnitude of the treatment difference (i.e., hazard ratio) between the treatment arms. The hazard ratio and its 95% confidence interval from the stratified Cox model with Efron's method of tie handling and with a single treatment covariate will be reported. Age and ISS stage will be used as the stratification factors in both the stratified log-rank test and the stratified Cox model. The test of the primary hypothesis will be assessed by evaluation of the treatment difference in PFS using the stratified log-rank test.

Since disease progression is assessed periodically, PD can occur any time in the time interval between the last assessment where PD was not documented and the assessment when PD is documented. For the primary analysis, for the subjects who have PD, the true date of disease progression will be approximated by the date of the first assessment at which PD is objectively documented per IMWG 2011, regardless of discontinuation of study drug. Death is always considered as a confirmed PD event. Subjects without documented PD/death will be censored at the last disease assessment date.

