In order to evaluate the robustness of the primary endpoint PFS per IMWG 2011 criteria by CAC blinded central review, we will perform two sensitivity analyses with a different set of censoring rules. The first sensitivity analysis is the same as the primary analysis except that it censors at the last disease assessment without PD when PD or death is documented after more than one missed disease assessment. The second sensitivity analysis is the same as the primary analysis except that it considers discontinuation of treatment or initiation of an anticancer treatment subsequent to discontinuation of study-specified treatments, whichever occurs later, to be a PD event for subjects without documented PD or death. The censoring rules for primary and sensitivity analyses are summarized in [Table 15](#) below. In case there are imbalances between treatment groups in disease assessment schedules or censoring patterns, additional PFS sensitivity analyses may be performed as supportive analyses, for

example: 1) A PFS analysis using time to scheduled disease assessment visit from randomization as opposed to actual disease assessment time; and, 2) Finkelstein’s (1986) likelihood-based score test [51] for interval-censored data, which modifies the Cox proportional hazards model for interval censored data in which the interval will be constructed so that the left endpoint is the date of the last disease assessment without documented PD and the right endpoint is the date of documented PD or death, whichever occurs earlier.

Table 15 Censoring Rules for Primary and Sensitivity Analyses of PFS

Situation	Primary Analysis	Sensitivity Analysis 1	Sensitivity Analysis 2
No PD and no death; new anticancer treatment is not initiated	Censored at last disease assessment	Censored at last disease assessment	Censored at last disease assessment if still on study therapy; progressed at treatment discontinuation otherwise
No PD and no death; new anticancer treatment is initiated	Censored at last disease assessment before new anticancer treatment	Censored at last disease assessment before new anticancer treatment	Progressed at date of new anticancer treatment
PD or death documented after ≤ 1 missed disease assessment	Progressed at date of documented PD or death	Progressed at date of documented PD or death	Progressed at date of documented PD or death

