For this protocol, there are no Tier 1 events. In addition, the broad clinical and laboratory AE categories consisting of the percentage of subjects with any AE, any drug related AE, any serious AE, any Grade 3-5 AE, an AE which is both Grade 3-5 and drug-related, an AE which is both drug-related and serious, dose modification due to AE, and who discontinued due to an AE, and death will be considered Tier 2 endpoints. 95% confidence intervals (Tier 2) will be provided for between-treatment differences in the percentage of subjects with events; these analyses will be performed using the Miettinen and Nurminen method (1985) [55], an unconditional, asymptotic method.

To properly account for the potential difference in follow-up time between the study arms, which is expected to be longer in the pembrolizumab containing arms, AE incidence density adjusted for treatment exposure analyses may be performed as appropriate. Based on emerging external data, the supportive analysis strategy for safety parameters may be modified to improve the integrity and efficiency of the design. Should this happen, the change will be documented in supplemental SAP, if not in a protocol amendment, at the earliest time before any unblinding of the data.

Table 17 Analysis Strategy for Safety Parameters

Safety Tier	Safety Endpoint	95% CI for Treatment Comparison	Descriptive Statistics
Tier 2	Any AE	X	X
	Any Grade 3-5 AE	X	X
	Any Serious AE	X	X
	Any Drug-Related AE	X	X
	Any Serious and Drug-Related AE	X	X
	Any Grade 3-5 and Drug-Related AE	X	X
	Dose Modification due to AE	X	X
	Discontinuation due to AE	X	X
	Death	X	X
	Specific AEs, SOCs (including ≥ 4 subjects in one of the treatment groups)	X	X
Tier 3	Specific AEs, SOCs (incidence < 4 subjects in all of the treatment groups)		X
	Change from Baseline Results (Labs, ECGs, Vital Signs)		X
† Adverse Experience references refer to both Clinical and Laboratory AEs. Note: SOC=System Organ Class; X = results will be provided.			

Time to Grade 3-5 AE

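### Table 15 Sensitivity Analysis 2 counts treatment stopped by the 03-JUL-2017 hold as PFS progression, which pulls the hazard ratio towards 1

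*Combined protocol and SAP*

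**What the plan says.** Section 8.0 states the effect of the hold: "All subjects must stop study treatment, complete the Discontinuation Visit and move into the long-term safety and survival follow-up per protocol". It closes with "Due to the current status of the study the statistical analysis of this section may be modified and will be reported in the CSR".

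Section 8.6.1 gives two sensitivity analyses whose purpose is to test how robust the primary PFS result is. The second, in the text, "considers discontinuation of treatment or initiation of an anticancer treatment subsequent to discontinuation of study-specified treatments, whichever occurs later, to be a PD event". This applies only where neither PD nor death has been recorded. Table 15 splits this into two rows:

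- No PD, no death, no new anticancer treatment: "Censored at last disease assessment if still on study therapy; progressed at treatment discontinuation otherwise".
- No PD, no death, new anticancer treatment started: an event on the date of that treatment.

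Neither the text nor the table looks at why treatment stopped. The primary rule is different. It dates PD "regardless of discontinuation of study drug" and censors subjects without PD or death at the last disease assessment, or at the last one before new anticancer treatment.

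**The concern.** Counting discontinuation as progression makes sense when stopping treatment may signal a failing patient. A regulatory hold gives no such signal: it stops everyone in both arms because of a calendar date. Read literally, Sensitivity Analysis 2 turns each subject who was progression-free and on treatment at the hold into a PFS event, unless PD or death is documented later.

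These added events say nothing about the treatment difference and could outnumber the real ones. A sound primary result, whether benefit or harm, would then look fragile in the analysis meant to support it. In a trial closed on safety data, dilution of a harm signal matters as much as dilution of a benefit.

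**Working it through.** **Inputs from the documents.** Section 8.9: 640 subjects, 1:1; exponential PFS with control median 25.5 months; HR 0.65; 18-month accrual; dropout 2% at 1 year and 5% at 4 years. Document History: protocol first issued 28-JUL-2015. Section 8.0: hold on 03-JUL-2017. The interval is 706 days, and 706/30.44 = 23.2 months. This is the longest possible time from first subject to hold.

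**Assumed.** Uniform accrual from that first date with all 640 enrolled; every progression-free subject still followed is on treatment at the hold; hazards unchanged afterwards; no new therapy unless stated; HR 1.25 as an example of harm.

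**The plan's own figure.** Events = 4(1.960 + 1.282)²/(ln 0.65)² = 4 × 10.51/0.1856 = 226.5, so 227, with 90.1% power. The model reaches 227 events at month 29.4, against about 30 in Table 18. At month 20 it gives 134 events where Table 18 has about 115. The plan states no accrual shape, and slower early accrual would lower the model's count.

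**Hand check, PFS cut-off at the hold.** In the control arm the model gives 91.9 events and 222.4 subjects still at risk at month 22, and 103.7 and 209.9 at month 24. Interpolating to 23.2:

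- events: 91.9 + 0.6 × 11.8 = 99.0
- stopped by the hold: 222.4 − 0.6 × 12.5 = 214.9
- ratio r = 214.9/99.0 = 2.17

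If the stops act as an added hazard common to both arms, the HR is roughly (θ + r)/(1 + r). For θ = 0.65 this is 2.82/3.17 = 0.89. For θ = 1.25 it is 3.42/3.17 = 1.08.

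**Simulation of the rule as written** (unstratified Cox; counts at true HR 0.65, where each row totals 629 events):

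| PFS cut-off after hold | Real PFS events | Hold stops | Share of events | True 0.65 becomes | True 1.25 becomes |
|---|---|---|---|---|---|
| 0 months | 168 | 461 | 73% | 0.89 | 1.08 |
| 6.2 months | 227 | 402 | 64% | 0.92 | 1.07 |
| 12 months | 629 − 354 = 275 | 354 | 56% | 0.95 | 1.04 |

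The primary rule returns 0.65 in each case. The distortion grows with a later cut-off although the share of hold stops falls. Subjects with later PD keep their PD date, while those still progression-free are scored back at the hold, and the better arm has more of the latter.

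**Variations, true HR 0.65.**

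- Accrual starting 3 months later: 0.91, 0.94 and 0.97 at the three cut-offs.
- Accrual starting 5.2 months later: 0.92, 0.96 and 1.00.
- Hold 16 to 23 months after first subject, cut-off at the hold: 0.94 to 0.89. If only half of those stopped become events: 0.89 to 0.83 (true 1.25 gives 1.08 to 1.12).
- A further 20% per year stopping earlier for other reasons: 0.91 to 0.98 as written, 0.80 to 0.76 with hold stops censored. The remaining gap from 0.65 comes from counting those earlier stops, which the rule was designed to do.
- An assumed 50% to 80% starting new therapy after the hold (median 2 months): about 0.92 to 0.89 as written, 12 months after the hold. Censoring only those without new therapy gives about 0.80 to 0.85 at 6.2 to 12 months. Applying the primary rule to all hold-stopped subjects returns 0.65.

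**The case against.** **The plan expects changes and already has routes for them.** This stands. A reader might infer from the last sentence of 8.0 that PFS and OS methods could be altered with no governing rule. The documents do not support that. The first paragraph of 8.0 requires a protocol amendment for changes to primary and key secondary hypotheses or their methods, an sSAP entry before any analysis for non-confirmatory changes, and clear identification of post hoc exploratory analyses in the CSR. The last sentence waives none of this. But a route for change is not a change: Table 15 still states the rule.

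**Only a supportive analysis is affected.** This also stands. A reader might infer that the hold corrupts the primary PFS test or its type I error. It does not, because the primary rule censors these subjects. What does follow is fewer primary events: new therapy after the hold censors subjects earlier. If an assumed 80% start new therapy, the model gives about 200 events 6.2 months after the hold, not 227. Nor does the hold wording show that disease follow-up ended. Flow chart footnote f says "Myeloma laboratory testing should be performed in the follow-up period for all subjects who discontinue study treatment for reasons other than disease progression", and 7.1.5.5 agrees.

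**The rule was meant to be conservative.** That is fair for stops that may reflect the patient's condition, but not for a stop imposed on both arms on one date.

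**The sizes rest on assumed dates.** True: the documents give no first-subject date, no number on treatment at the hold and no rate of new therapy. The direction was the same in every setting tried.

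**Conclusion.** Sensitivity Analysis 2 is wrong as written for a trial in which all treatment was stopped by regulatory action. Under the 8.9 assumptions and the earliest possible start, it moves a true HR of 0.65 to about 0.89 to 0.95 and a true HR of 1.25 to about 1.04 to 1.08, with or without new therapy after the hold. Later accrual pushes 0.65 closer to 1; if only half of the stopped subjects become events, the movement is smaller (0.83 to 0.89).

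These figures illustrate the mechanism. They do not show that any reported result was distorted: no observed counts are in the documents, and the sSAP may already contain the remedy. The primary PFS rule, Sensitivity Analysis 1 and the type I error are not touched by this defect.

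**What to change.** Add to the Sensitivity Analysis 2 column of Table 15:

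> Subjects without PD or death whose study treatment was stopped because of the 03-JUL-2017 hold are handled by the primary-analysis censoring rule (censored at the last disease assessment, or at the last disease assessment before any new anticancer treatment); discontinuation or new treatment before the hold is handled as stated.

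The rule has to cover subjects who start new therapy after the hold. Otherwise they remain events in the next row of the table and much of the distortion stays.

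Record this as a dated change by the route in the first paragraph of 8.0, or label it post hoc in the CSR if analysis has begun. If the sSAP already contains such a rule, a cross-reference is enough.

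The cost is one sentence and no new data. The downside is that, for hold-stopped subjects, Sensitivity Analysis 2 no longer differs from the primary analysis, so it tests robustness only to discontinuation and new therapy before the hold.

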8.1 Statistical Analysis Plan Summary

Key elements of the statistical analysis plan are summarized below; the comprehensive plan is provided in Sections 8.2 through 8.12.

Study Overview	Design	Phase III Study of Lenalidomide and Low-dose Dexamethasone with or without Pembrolizumab in Newly Diagnosed and Treatment-Naïve Multiple Myeloma.
Treatment Assignment	Approximately 640 subjects with treatment-naïve multiple myeloma will be randomized in a 1:1 ratio between two treatment groups. The two treatment arms are as follows:	
	Treatment Arm	Treatment Dose and Schedule
	Treatment Arm A*	Pembrolizumab 200 mg + lenalidomide + low-dose dexamethasone
	Treatment Arm B*	Lenalidomide + low-dose dexamethasone
		*This is an open label study Stratification factors are 1) age (<75 years vs ≥ 75 years) and 2) ISS stage (I or II vs. III).
Analysis Populations	Efficacy: Intention-to-treat (ITT) population. Safety: All Subjects as Treated (ASaT)	
Primary Endpoint	1. Progression-free survival (PFS) – per IMWG 2011	
Secondary Endpoint	2. Overall Survival (OS)	
Statistical Methods for Key Efficacy Analyses	The primary hypothesis will be evaluated by comparing pembrolizumab in combination with SOC (lenalidomide +low-dose dexamethasone) versus SOC (lenalidomide + low-dose dexamethasone) on PFS using a stratified log-rank test. Estimation of the hazard ratio will be done using a stratified Cox regression model. Event rates over time will be estimated within each treatment group using the Kaplan-Meier method.	
Statistical Methods for Key Safety Analyses	The analysis of safety results will follow a tiered approach. The tiers differ with respect to the analyses that will be performed. No Tier 1 events are defined for this study. Tier 2 parameters will be assessed via point estimates with 95% confidence intervals provided for between-group comparisons; only point estimates by treatment group are provided for Tier 3 safety parameters. The between-treatment confidence intervals will be calculated using the Miettinen and Nurminen method. No formal treatment comparisons with p-values will be carried out.	
Interim Analyses	One efficacy interim analysis for PFS will be performed in this trial. Results will be reviewed by a DMC for evaluation of superiority as well as a non-binding futility assessment. This interim analysis will be conducted after all subjects have been enrolled and approximately 115 PFS events have been observed; details are provided in Section 8.7.	


Multiplicity
	
The family-wise type I error rate for this study is strongly controlled at 2.5% (one-sided).
 
For the PFS efficacy hypothesis, a Hwang-Shih-DeCani alpha-spending function with the gamma parameter (-8) is constructed to implement group sequential boundaries that control the type I error rate. For the PFS futility hypothesis, a Hwang-Shih-DeCani beta-spending function with the gamma parameter (-4) is constructed to implement group sequential boundaries that control the type II error rate. Further details of the interim analysis strategy can be found in Section 8.72.
 
For the OS hypothesis, there will be only one analysis when ~ 195 OS events are observed. The secondary OS hypothesis will be tested sequentially with one-sided alpha level of 2.5% if pembrolizumab (MK-3475) in combination with SOC is superior to the SOC in PFS and hence no multiplicity adjustment will be required.

Sample Size and Power
	
The planned sample size is approximately 640 subjects. The primary endpoint of the study is PFS. The expected median PFS time in the control group is 25.5 months. For PFS, based on 227 events, the study has 90% power to detect a hazard ratio of 0.65 (pembrolizumab in combination with SOC vs. SOC) at alpha = 2.5% (one-sided). For OS, based on 195 events, the study has ~ 70% power to detect a hazard ratio of 0.70 (pembrolizumab in combination with SOC vs. SOC) at alpha = 2.5% (one-sided).

